#### 5.2 Exclusion Criteria

Patients are ineligible to be included in the study if they:

- [1] Have a known DNA repair mutation (minimum list of genes that must be mutation negative for inclusion: ATM, BARD1, BRCA1, BRCA2, BRIP1, CDK12, CHEK1, CHEK2, FANCL, PALB2, RAD51B, RAD51C, RAD51D, RAD54L). In addition, patients who have not completed germline and somatic testing to rule out such a mutation are ineligible until they have completed testing. If tissue or liquid ctDNA sequencing was not previously done, testing using the Foundation One liquid biopsy test or an equivalent FDA-approved test is acceptable as standard of care.
  - DNA repair mutation variant of unknown significance (VUS) allowed.
- [2] Have had known active central nervous system (CNS) metastases and/or carcinomatous meningitis.
- [3] Have symptomatic uncontrolled brain metastases. A scan to confirm the absence of brain metastases is not required. The patient can receive a stable dose of corticosteroids before and during the study as long as these were started at least 4 weeks prior to treatment. Patients with spinal cord compression unless considered to have received definitive treatment for this and evidence of clinically stable disease for 28 days.
- [4] Have had prior olaparib, rucaparib, or other PARP inhibitor.
- [5] Have had major surgery within 2 weeks of dosing of investigational agent.
- [6] Have had palliative radiation or another biological cancer therapy within 3 weeks prior to the first dose of study drug (2 week wash out required).
- [7] Are receiving any systemic chemotherapy or radiotherapy within 3 weeks prior to study treatment.
- [8] Have received other investigational drugs within 14 days prior to enrollment.
- [9] Is expected to require chemotherapy or radiation for pain palliation in the next 12 weeks.

- [10] Have used or plan concomitant use of the following medications in the past 6 months prior to enrollment: 5-alpha reductase inhibitors unless subject has been taking stable dose of medication for prior 6 months.
- [11] Concomitant use of known strong CYP3A inhibitors (eg. itraconazole, telithromycin, clarithromycin, protease inhibitors boosted with ritonavir or cobicistat, indinavir, saquinavir, nelfinavir, boceprevir, telaprevir) or moderate CYP3A inhibitors (eg. ciprofloxacin, erythromycin, diltiazem, fluconazole, verapamil). The required washout period prior to starting study treatment is 2 weeks. See the following link for a complete list of known CYP3A inhibitors:

https://www.fda.gov/drugs/drug-interactions-labeling/drug-development-and-drug-interactions-table-substrates-inhibitors-and-inducers

[12] Concomitant use of known strong (eg. phenobarbital, enzalutamide, phenytoin, rifampicin, rifabutin, rifapentine, carbamazepine, nevirapine and St John's Wort ) or moderate CYP3A inducers (eg. bosentan, efavirenz, modafinil). The required washout period prior to starting study treatment is 5 weeks for enzalutamide or phenobarbital and 3 weeks for other agents. See the following link for a complete list of known CYP3A inhibitors:

https://www.fda.gov/drugs/drug-interactions-labeling/drug-development-and-drug-interactions-table-substrates-inhibitors-and-inducers

- [13] Have moderate or severe cardiovascular disease:
  - Has the presence of cardiac disease, including a myocardial infarction within six months prior to study entry, unstable angina pectoris, New York Heart Association Class III/IV congestive heart failure, or uncontrolled hypertension.
  - Resting ECG indicating uncontrolled, potentially reversible cardiac conditions, as judged by the investigator (eg., unstable ischemia, uncontrolled symptomatic arrhythmia, congestive heart failure, QTc prolongation >500 ms, electrolyte disturbances, etc.), or patients with congenital long QT syndrome.
- [14] Have uncontrolled intercurrent illness, including but not limited to ongoing or active infection, symptomatic congestive heart failure, unstable angina pectoris, cardiac arrhythmia, or psychiatric illness/social situations that would limit compliance with study requirements.
- [15] Have other malignancy unless curatively treated with no evidence of disease for ≥5 years except adequately treated non-melanoma skin cancer.
- [16] Have persistent toxicities (>Common Terminology Criteria for Adverse Event (CTCAE v5.0) grade 2) caused by previous cancer therapy, excluding alopecia.
- [17] Patients with myelodysplastic syndrome/acute myeloid leukemia or with features suggestive of MDS/AML.
- [18] Patients considered a poor medical risk due to a serious, uncontrolled medical disorder, non-malignant systemic disease or active, uncontrolled infection. Examples

include, but are not limited to, uncontrolled ventricular arrhythmia, recent (within 3 months) myocardial infarction, uncontrolled major seizure disorder, unstable spinal cord compression, superior vena cava syndrome, extensive interstitial bilateral lung disease on High Resolution Computed Tomography (HRCT) scan or any psychiatric disorder that prohibits obtaining informed consent.

- [19] Patients unable to swallow orally administered medication and patients with gastrointestinal disorders likely to interfere with absorption of the study medication.
- [20] Immunocompromised patients, e.g., patients who are known to be serologically positive for human immunodeficiency virus (HIV).
- [21] Patients with known active hepatitis (i.e. Hepatitis B or C).
- [22] Previous allogenic bone marrow transplant or double umbilical cord blood transplantation (dUCBT).
- [23] Patients with a known hypersensitivity to olaparib or any of the excipients of the product.

#### 5.3 Inclusion of Minorities and Women and Children

Since prostate cancer is only a disease of men, only male patients will be enrolled. Men from all ethnic groups are eligible for this trial. The Sidney Kimmel Comprehensive Cancer Center at Johns Hopkins serves a prostate cancer population in which approximately 25% of these patients are African Americans. We anticipate that enrollment in this study will be reflective of our usual patient population. Minority patients who meet the eligibility requirements will be actively recruited to participate in the study. This study was designed to encourage minority accrual but was not designed to measure differences in racial or ethnic populations.

#### 6.0 REGISTRATION

# 6.1 General Guidelines

Potential study subjects will be identified and screened by the study team. Eligible patients will be consented prior to treatment initiation. Eligible, consented patients will be entered on study centrally at the Sidney Kimmel Comprehensive Cancer Center at Johns Hopkins by the Lead Study Coordinator. Patient names and identifying information will only be linked in the CRMS (Clinical Research Management System) database, which is accessible through a password-protected encrypted university server. All sites should email [name] [contact] to verify slot availabilities.

Issues that would cause treatment delays should be discussed with [name]. If a patient does not receive protocol therapy within 7 days following registration, the patient's registration on the study may be canceled. The Study Coordinator should be notified of cancellations as soon as possible.

# 6.2 Registration Process

Eligible patients will be entered on study centrally at the Sidney Kimmel Comprehensive Cancer Center at the Johns Hopkins University by the Lead Study Coordinator. All sites should email [name] at [name] to verify drug availabilities. The Registration Form, and Eligibility Worksheet will be supplied to each participating site.

If a patient does not receive protocol therapy following registration, the patient's registration on the study may be canceled. The Coordinating Center should be notified of cancellations as soon as possible.

To register an eligible, consented patient, the following documents should be completed by the Research Nurse or Study Coordinator and emailed to the monitors [name] at [contact].

- Signed patient consent form
- Eligibility Screening Checklist
- Copies of the prostate cancer pathology report
- Copies of PSA and Testosterone results to determine eligibility
- Copy of required screening labs and scans
- Physician note that indicated prior therapies
- Other materials may also be sent if considered pertinent for confirming patient eligibility

The Research Nurse or Study Coordinator at the participating site will then email the monitors to verify eligibility. To complete the registration process, the monitors will:

- Assign a patient study number
- Register the patient on the study
- Email the registration confirmation to the participating site

# 7.0 TREATMENT/INTERVENTION PLAN

The following assessments and procedures will occur during the study. A schedule of assessments is provided in **Section 7.1** 

# 7.1 Study Calendar

Required Studies	Pre-study 	1 cycle = 28 days		EOT 	LONG TERM FU 			
	Screening	C1D1 	C1D8	C1D15 	C1D22 	CnDn 		
Visit Windows (days) 	-28	+/-3	+/-3	+/- 3	+/-3	+/- 3	-28	+/-28
TREATMENT								
Olaparib		X	X	X	X	X		
Ascorbic acid 		X	X	X	X	X		
ELIGIBILITY								
Inclusion/exclusion review	X							
HRR status 	X							
Informed consent	X							
ECG	X							
PHYSICAL								
Medical and Cancer History	X							
Physical Exam, Weight and ECOG 	X	X	X	X	X	X	X	X
Vital Signs 	X	X	X	X	X	X	X	X
AE/Toxicity Notation 		X	X	X	X	X	X	X
Concurrent meds 	X	X	X	X	X	X	X	X
LABORATORY								
Chemistry 	X	X	X	X	X	$X^7$	X	X
Hematology 	X	X				$X^7$	X	X
Urinalysis	X							
INR and PT/APTT 	X							
Urine Creatinine 	X 	X 				X 	X 	
Testosterone	X							
PSA 	X	X				$X^7$	X	X
G6PD 	X							
CORRELATIVE								
Blood Samples 	NA	X 				X 	$X^{10}$	
Urine Samples 	NA	$X^{11}$				$X^{11}$	$X^{11}$	
Optional Biopsy (Encouraged)	X 	N/A				X 		
DISEASE ASSESSMENT								
Radiologic Evaluation/ RECIST 1.1  or PCWG2	X 					X 	X 	
LONG TERM FOLLOW-UP 								X 

- Longer delays to be approved by the study sponsor. IRB approval is required for all eligibility waivers prior to enrollment. The window for the baseline Radiologic Evaluation/RECIST 1.1 is 6 weeks prior to C1D1.
- Each treatment cycle is 4 weeks (28 days). Ascorbic Acid dosing must be 2 times per week except week 1 when Olaparib is giving alone. The first infusion must occur on day 1 of each cycle and the second infusion can occur any other day during the week as long as it is at least 24 hours from the prior infusion.
- Ports are recommended but not mandatory due to the frequency of infusion.
- 4 After screening, physical exams may be limited as indicated by symptoms. ECOG Eastern Cooperative Oncology Group performance status. Physical exam (including vital signs and weight), ECOG status, AE/Toxicity notation and concurrent medication review have a -3 day window of day 1 of the cycle.
- Vital signs will be collected prior to infusion. Vital signs include temperature, blood pressure, respiration rate, and heart rate. Height is collected prestudy only. There is a -3 day window of day 1 of each cycle that the vital signs can be collected within.
- 6 Clinical Hematology: CBC with differential ANC, ALC, AEC, and platelet count; Serum Chemistry: sodium, potassium, chloride, bicarbonate, glucose, BUN, creatinine, ALT, AST, alkaline phosphatase, total bilirubin, total protein, albumin, calcium.
- Safety labs and PSA may be collected within a window of up to 3 days prior to scheduled visit/dosing. As of Cycle 2 and further cycles: at Day 1 visit, hematology and chemistry should be collected per hold parameters; at Days 8, 15, and 22 visits, only chemistry will be collected per hold parameters (hematology does not need to be drawn on Days 8, 15, and 22 unless clinically indicated). After C1D1, PSA is collected at CnD1 only (i.e., not weekly).
- 8 Urine creatinine will be collected at C1D1, C2D1 (4 weeks), C4D1 (12 weeks), and at EOT.
- G6PD testing: Red blood cell hemolysis may occur in people found to be deficient in the G6PD enzyme.
- Up to 50mL of whole blood will be collected for ctDNA analysis at each time point. Blood samples should be drawn at screening (or pre-dose C1D1), C2D1 post infusion (4 weeks), C4D1 (12 weeks) post infusion, and at EOT. Bloods do not need to be collected at C1D1 if they were collected within 7 days prior to the visit. γ H2AX will also be assessed at C1D1, C1D8, C2D1, C4D1 and progression.
- Urine samples of up to 15mL will be collected to assess F2-isoprostanes and 8-oxo-2'-deoxyguanosine at screening (or pre-dose C1D1), C2D1 (4 weeks), C4D1 (12 weeks), and at EOT. Urine samples do not need to be collected at C1D1 if they were collected within 5 days prior.
- 12 Research samples will be collected at the discretion of the PI based on availability of supplies and safety of patient and staff. An optional biopsy at baseline and at C4D1 (+/- 2 weeks) will be performed to look for γH2AX in tissue.
- CT scan (chest/abdomen/pelvis or MRI if patient has contrast allergy) and bone scan to be assessed at baseline and every 12 weeks (+/- 1 week), and at EOT (if clinically indicated by PI/Sub-I).
- In order to minimize the need for research-only in-person visits, telemedicine visits may be substituted for in-person clinical trial visits or portions of clinical trial visits where determined to be appropriate and where determined by the investigator not to increase the participants risks. Prior to initiating telemedicine for study visits, the study team will explain to the participant what a telemedicine visit entails and confirm that the study participant is in agreement and able to proceed with this method. Telemedicine acknowledgement will be obtained in accordance with the Guidance for Use of Telemedicine in Research. In the event telemedicine is not deemed feasible, the study visit will proceed as an in-person visit. Telemedicine visits will be conducted using HIPAA compliant methods approved by the Health System and within licensing restrictions.
- There is a -7 day window to draw C1D1 labs.
- The EOT visit must occur within 28 days of the last dose of ascorbic acid or olaparib, whichever is later.

- Subjects who discontinued study treatment without documented disease progression should continue to be monitored for disease status by radiologic imaging. Disease monitoring should continue to be assessed every two months (+/- 2 weeks) until: 1) start of a new antineoplastic therapy (information of the new cancer therapy will be collected), 2) disease progression, 3) death, 4) withdrawal of consent, or 5) study closure, whichever occurs first. Survival status and subsequent therapies will be collected during long term follow-up (LTFU) every 6 months (+/- 4 weeks) from the date of last treatment, by phone or chart review, for 3 years or until study closure. Gather date of death, date of radiographic and/or PSA progression, start and stop dates for subsequent therapies.
-  INR and PT/APTT will be performed at baseline and at subsequent timepoints if clinically indicated.
- HRR status will be determined by evaluating patients for mutations in the genes ATM, BARD1, BRCA1, BRCA2, BRIP1, CDK12, CHEK1, CHEK2, FANCL, PALB2, RAD51B, RAD51C, RAD51D, and RAD54L. DNA repair mutation variants of unknown significance will be allowed. Mutation status of these genes will be determined with standard of care tests, such as Invitae, Color, or Foundation One, using germline and somatic testing. Tissue (prostatectomy or metastatic biopsy for somatic or germline testing), blood (somatic or germline) or saliva (germline) are all acceptable for standard of care testing prior to enrollment. Germline test results will be confirmed with somatic testing. If tissue is not available, confirmation testing using Foundation One liquid biopsy test or an equivalent FDA-approved test is acceptable. The type of test and results for each individual patient will be captured in the appropriate CRF in the database.
-  For all subsequent cycles, patients will repeat the four visits listed for Cycle 1 (CnD1, CnD8, CnD15, CnD22).

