#### 7.2 Screening/Pretreatment Assessment (up to Day -28)

Before initiating any screening activities, the scope of the study should be explained to each patient. Patients should be advised of any known risks inherent to the planned procedures, any alternative treatment options, their right to withdraw from the study at any time for any reason, and their right to privacy. After this explanation, patients should be asked to sign and date a Notice of Privacy Practice research authorization/HIPAA form and an IRB-approved statement of informed consent that meets the requirements of the Code of Federal Regulations (Federal Register Vol. 46, No. 17, January 27, 1981, part 50).

The following assessments will be performed at the screening visit:

- Obtain informed consent and research authorization.
- Record demographics (including age) and medical history (including prior treatment for prostate carcinoma).
- Conduct physical exam (including vital signs, height/weight).
- Obtain history regarding prior treatment history for prostate cancer (including history of ADT, and history of radiation therapy or other local therapy).
- Obtain histologic/radiographic confirmation of disease. If radiographic studies have not been performed within 6 weeks prior to Cycle 1 Day 1, they must be obtained as part of screening.
- Perform laboratory tests: complete blood count w/diff, PSA, comprehensive metabolic panel, urinalysis, G6PD, testosterone.
- Baseline ECG
- Confirmation of 25% PSA rise on prior therapy.
- Determine suitability for olaparib and ascorbate therapy.
- Discuss concurrent medications.

Relevant information should be documented for registration and monitoring purposes. The institutional registration should be finalized, and appropriate documents faxed or emailed to the lead site/sponsor per **Section 6.0**.

Information for patients who do not meet the eligibility criteria to participate in this study (i.e. screening failures) should be captured in consortium database at the pretreatment assessment.

For any subject that has a DNA repair gene mutation identified during screening and is therefore not eligible for this trial will be referred to medical genetics for counseling and consideration of further targeted testing to determine if the identified mutation is present in the germline.

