# 7.9 Expected Adverse Events

# 7.9.1 Ascorbic Acid

Too rapid intravenous administration of the solution may cause temporary faintness or dizziness.

The most common side effects of ascorbic acid include: pain and swelling at administration sites, nausea, vomiting, diarrhea, dry mouth, loss of appetite, muscle weakness, dizziness, headache, phlebitis, hypertension, fatigue, and leakage of protein.

Less common side effects of ascorbic acid include: acute and chronic nephropathy, kidney stones, renal failure, hypernatremia, hypoalbuminemia, hyperglycemia, and hypokalemia.

Of note, it has been reported that patients with a history of glucose-6-phosphate dehydrogenase deficiency experienced hemolysis.

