# 8.0 DOSING DELAYS/MODIFICATIONS

# 8.1 Dosing Delays

All scheduled cycles occur over a 28-day period. If necessary, treatment may be delayed for up to 4 weeks. If treatment is delayed more than two weeks, the Principal Investigator must be contacted for further instructions on continued treatment. Additional delays or modifications to the treatment schedule must be approved by the Protocol Chair. When the delay is due to toxicity, then the next cycle may begin with a dose reduction.

Ascorbic acid will be withheld for the following drug-related toxicities:

- $Cr \ge 1.6 \times ULN$  (for patients with  $Cr \ge 1.6 \times ULN$ , calculated or measured creatinine clearance must be  $\ge 50 \text{ mL/minute}$  (Cockcroft-Gault))
- Common Terminology Criteria for Adverse Events (CTCAE) Grade 3 or 4 non-hematologic toxicity excluding asymptomatic electrolyte aberrations
- Any AE, laboratory abnormality, or intercurrent illness that, in the judgement of the investigator, warrants delaying the dose of study medication

Olaparib will be withheld for the following drug-related toxicities:

Absolute neutrophil count
 Platelets
 Hemoglobin
 Total bilirubin
 AST (SGOT)/ALT(SGPT)
 ≤ 750/ mm³, see Table 8
 ≤ 8 hgb, If < 10, see Table 7

 ≥ 1.5XULN
 ≥ 2.5 x ULN (<5x ULN if with known liver m

• AST (SGOT)/ALT(SGPT)  $\geq 2.5 \text{ x ULN (<}5\text{x ULN if with known liver metastases}$  provided bilirubin is normal)

- Common Terminology Criteria for Adverse Events (CTCAE) Grade 3 or 4 non-hematologic toxicity excluding asymptomatic electrolyte aberrations
- Any AE, laboratory abnormality, or intercurrent illness that, in the judgement of the investigator, warrants delaying the dose of study medication

If dosing parameters for Ascorbic Acid are not met, study participants may continue with olaparib therapy. If dosing parameters for olaparib or are not met, study participants may continue with Ascorbic Acid therapy. Dose interruptions are allowed as required, for a maximum of 4 weeks. Patients who require an interruption in olaparib or ascorbic acid for >4 weeks due to toxicity must permanently discontinue study drug unless an exemption is granted by the protocol chair (Refer to section 13.6 for stopping rule). Where toxicity reoccurs following re-challenge with study treatment, then the patient should be considered for dose reduction or must permanently discontinue study treatment per investigator judgement.

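### G6PD is tested at screening and hemolysis is warned of twice, but no eligibility criterion or ascorbate dosing rule in the protocol acts on the result

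*Combined protocol and SAP*

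**What the plan says.** G6PD is marked at screening in the Study Calendar (7.1) and appears in the Section 7.2 list: "Perform laboratory tests: complete blood count w/diff, PSA, comprehensive metabolic panel, urinalysis, G6PD, testosterone". Footnote 9 of the calendar explains the test: "Red blood cell hemolysis may occur in people found to be deficient in the G6PD enzyme". Section 7.9.1, on expected adverse events of ascorbic acid, reports that "patients with a history of glucose-6-phosphate dehydrogenase deficiency experienced hemolysis".

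The Section 5.2 list that opens "Patients are ineligible to be included in the study if they" has 23 items, and none names G6PD or hemolysis. Nor does any of the 13 inclusion criteria in Section 5.1, including the organ and marrow function list in [11].

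Three provisions could reach a deficient man without naming the condition:

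- Section 7.2 has a screening step: "Determine suitability for olaparib and ascorbate therapy". It gives no criteria.
- Exclusion [18] covers "Patients considered a poor medical risk due to a serious, uncontrolled medical disorder, non-malignant systemic disease or active, uncontrolled infection". Its examples do not include G6PD deficiency.
- Section 8.1 lets ascorbate be withheld for "Any AE, laboratory abnormality, or intercurrent illness that, in the judgement of the investigator, warrants delaying the dose of study medication".

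Section 6.2 requires a "Copy of required screening labs and scans" to be sent in before registration, so the G6PD value should be available when eligibility is verified.

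**The concern.** The protocol names a harm, requires a test that identifies who is exposed to it, and then attaches no consequence to the answer. A site that applied the written eligibility criteria and the objective ascorbate holds to the letter could infuse a man whom the trial's own test had flagged. In a multi-center trial, sites may also handle the same result differently, and the monitors who verify eligibility have no G6PD criterion in the protocol to check against.

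The protocol does state a bar where it intends one. Sections 7.3.1 and 7.7 exclude men on warfarin outright, and 7.7 gives an interaction with ascorbic acid as the reason. G6PD deficiency has a test and two warnings but no equivalent sentence.

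The stake is patient safety. The primary analysis, the sample size and the error rates are unaffected.

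**Working it through.** There is no stated figure to reproduce. The check is a reading of every place where a rule could sit, plus simple dose arithmetic.

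**1. Mentions.** The test is listed in two places (7.1 and 7.2). Hemolysis in deficient patients is warned of in two places (7.1 footnote 9 and 7.9.1).

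**2. Eligibility.** 13 inclusion + 23 exclusion = 36 criteria, of which 0 use the result. The hypersensitivity exclusion [23] concerns olaparib only.

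**3. Section 8 rules for ascorbate.** Section 8.1 gives three grounds for withholding it: creatinine at or above 1.6 x ULN, grade 3 or 4 *non-hematologic* toxicity, and investigator judgement. Section 8.2.1 allows one reduction, to 0.75 g/kg, and does not mention G6PD. No objective ascorbate hold is triggered by a G6PD result or by anemia.

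**4. On-treatment safeguards.** Setting the provisions side by side:

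| Provision | What it does | Limit for this purpose |
|---|---|---|
| 7.1, 7.3.1 | Weekly chemistry including total bilirubin; weekly AE review | Acts after exposure |
| 7.3.1, Appendix D | Work-up when bilirubin reaches 2 x ULN | Written for liver injury |
| 8.1 | Olaparib held at hemoglobin of 8 or below, or bilirubin of 1.5 x ULN or above | Ascorbate may continue |
| Table 7 | Cause of anemia investigated when hemoglobin is under 10 g/dL | Dose actions are for olaparib |
| 7.4 | Patient removed when an 8.1 toxicity is unresolved after 2 weeks or recurs at the lower dose | Exception where clinical benefit is strong |
| 7.3.1 | Blood count on Day 1 of each cycle, or when clinically indicated | None scheduled on C1D8, C1D15 or C1D22 |

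Olaparib itself often causes anemia: grade 3-4 in 20% of the prostate cohort in 4.2.6 and in 17.4% in Table 1. A hemolytic fall in hemoglobin could therefore be put down to olaparib at first.

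**5. Scheduled ascorbate before the C2D1 blood count.** The sections differ on the first dose, so both readings are shown.

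- Start on C1D8 (7.6.2; 7.1 footnote 2), twice weekly in weeks 2 to 4: 3 x 2 = 6 infusions. Dose: 0.25 + 0.5 + 0.75 + 3 x 1 = 4.5 g/kg. At 75 kg: 4.5 x 75 = 337.5 g.
- Start on C1D1 (Schema; Table 2), twice weekly in weeks 1 to 4: 4 x 2 = 8 infusions. Dose: 0.25 + 0.5 + 0.75 + 5 x 1 = 6.5 g/kg. At 75 kg: 6.5 x 75 = 487.5 g.

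These are scheduled doses. They do not measure the risk of hemolysis.

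**6. How often it could arise.** The documents give no prevalence of G6PD deficiency. For an assumed prevalence p, the chance that at least one of n men is deficient is 1 - (1 - p)^n.

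| Assumed p | n = 12 | n = 15 |
|---|---|---|
| 1% | 11% | 14% |
| 5% | 46% | 54% |
| 10% | 72% | 79% |

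Each entry is an upper bound on the chance of enrolling a deficient man, because it supposes that nobody acts on a deficient result.

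**The case against.** The strongest reply is that the result does have a decision step. The suitability judgement stands in the same Section 7.2 list as the G6PD test, a careful investigator would probably use it, and Section 6.2 puts the screening labs before the monitors. The eligibility worksheet and checklist named in 6.2, and the ascorbic acid brochure on which 4.2.4 relies, are not among the documents and could contain an explicit rule. This stands to the extent that the point can be made only of the protocol text. It does not supply a criterion there: the suitability step has no content, and exclusion [18] does not name the condition.

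The on-treatment safeguards also count. Table 7 requires the cause of anemia to be investigated, with a G6PD result already on file. Section 8.2 requires adverse events possibly related to either drug to settle to grade 1 or baseline before dosing resumes. Section 7.3.1 adds weekly laboratory and toxicity monitoring for men with creatinine clearance of 51-100 mL/min, although it does not say that a blood count is included. All of these act after a deficient man has been infused, so they reduce the harm without replacing a screening rule.

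Three stronger readings are tempting and are not supported:

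- A reader might infer that ascorbate could run on for four weeks of unresolved anemia, from the 4-week limits in 8.1 and 8.2.2.3. The 2-week removal rule in 7.4 applies sooner, subject to its clinical-benefit exception.
- A reader might use the remark in 4.2.7 on few adverse events among suitably screened users of IV ascorbate as a condition this trial fails to meet. That passage does not say what the screening was or that it included G6PD.
- A reader might infer that deficient men will be treated. The documents show only that no written criterion prevents it.

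**Conclusion.** The point holds for the protocol as written. G6PD is a required screening test tied to a harm named twice, and 0 of 36 eligibility criteria and no Section 8 ascorbate rule use the result. Within that text, keeping a deficient man off ascorbate depends on three discretionary steps, and the remaining safeguards are partial and follow exposure.

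The size that can be stated is the scheduled exposure before the first planned blood count after ascorbate begins: 6 infusions (4.5 g/kg) with a C1D8 start, or 8 (6.5 g/kg) with a C1D1 start, assuming full titration with no holds and no count drawn for clinical reasons. The probability of hemolysis cannot be estimated from the documents. The conclusion is limited by the absence of the worksheet, checklist and brochure; if one of them already bars deficient men, the change would only bring the protocol into line. The sponsor should make the change.

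**What to change.** Add to Section 5.2: *Have G6PD deficiency on the screening test (per the local laboratory's reference range).* State that the result is reviewed before registration and before any ascorbate is given. The sponsor may prefer a single cut-off across sites, since local ranges can differ; what matters is that one is written down.

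The cost is one line. No test is added, screening labs already go in under 6.2, and the 12-patient design with its threshold of 2 responses does not change. The downside is an occasional extra screen failure. Under the assumed prevalences, enrolling 15 men requires 15/(1 - p) otherwise eligible men: 15.2 at 1%, 15.8 at 5% and 16.7 at 10%. That is about 0.2 to 1.7 extra men, at an expected accrual of one a month.
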